Endodontic therapy might also damage the IAN. Several mechanisms have been proposed, including (1) neurotoxic effect from root canal filling material penetrating the IAN (**Pogrel et al 2007;Valmaseda et al 2001**); (2) mechanical pressure on the nerve caused by overextension of filling material or over

instrumentation with hand or rotary files (**Pogrel et al 2007; Valmaseda et al 2001**); IAN damage has been suggested to occur in 1% of mandibular premolars that receive root canal treatment (**Escoda et al 2007**).

There is an incidence for nerve injury during dental implant placement, resulting from the poor assessment of bone length or excessive length of implant bodies. Therefore to avoid damage of inferior alveolar nerve, it is important to assess the mandibular canal location in the mandible and edentulous space that represent the missing tooth. (**Jui-Ting Hsu et al 2013**)

The nerve injury is unfavorable consequences for the patient (**Escoda et al 2007; Burstein et al 2008**). If an intimate relation exists, this may have clinical relevance and risk of nerve injury implications in relation to root canal treatment and dental placement of mandibular premolars and molars

Rational of the Study

The linear relation between mandibular premolar and mandibular molars to inferior alveolar canal is not correlated; this study may help to reduce IAN injury during dental and surgical procedures.

Statement of the Problem

Direct nerve damage may be caused by placement of implants, or surgical extraction, or endodontic treatment. All of these may cause temporary or permanent damage to the IAN (**poveda et al 2006; Lvovsky et al 2018**). These procedure are invasive, and the nerve may be close to the root apex of the posterior teeth. So the clinical relation between inferior alveolar canal and apices of roots of mandibular premolar and molar is important to avoid nerve damage.

Review of literature

List of main databases used in search:

- Pubmed
- Google Scholar

Keywords:

- Cone-beam computed tomography- Inferior Alveolar Nerve-Mandibular Premolars- Mandibular Molars -Nerve Injury.

Various dental procedures distal to mental foramen pose a potential iatrogenic cause of inferior alveolar nerve injury (**Escoda et al 2007**), The dental procedures include the surgical and non-surgical procedural, they include the endodontic treatment, implant placement, or extraction of third mandibular molar (**kovisto et al 2011**).

In endodontic treatment obturation, gutta percha is traditionally considered an inert root-filling material, the paresthesia's cases involving gutta percha results from overfill of thermoplastic gutta-percha. If the sealers are excluded from the apices in the mandibular canal space, it can cause nerve injury (**Hiremath et al 2016**).

Injury to the IAN has also been shown with extraction of mandibular third molars (frequency of 1.3%), suggesting that teeth are often close to the nerve. In patients with mental nerve injury, extraction and implant placement have been implicated in 63% of cases with problems (**Kalladka et al 2008**). **Hidenobu et al** reported the relation of third mandibular molar and position of the inferior alveolar nerve without reporting the root apices relation to the nerve.

One of the dentists' objectives is to retain the nature tooth, but if loss of tooth structure, periodontal disease, or trauma is severe, the tooth might be un-restorable. To replace a lost tooth, the treatment option is placement of dental implant to replace the extracted tooth. Immediate implant placement, with apical penetration of the

implant 4–5 mm beyond the previous position of the tooth root into bone for stabilization, can cause injury to the nerve. If the IAN is in close proximity to the root apex of the tooth extracted, implant placement 4–5 mm below the apex of the socket of extracted tooth might cause injury to the nerve. Nerve damage has been reported in 17% of implant cases (**Kubilius et al 2004**). Paresthesia can be as high as 13% in the posterior mandible from implants (**Burstein et al 2008**). Neurosensory problems can be as high as 52% in patients who have received a dental implant (**Kovisto et al 2011**). Although IAN damage is infrequent and the prevalence is not well-defined, it is a serious situation that has unfavorable complication for the patient. Before going procedures with potential for IAN injury, it is critical to determine the location of the inferior alveolar canal with respect to the surrounding structures to avoid injury of anatomical structure (**Burstein et al 2008**).

Jerjes et al 2005 has reported also that the paresthesia of inferior alveolar nerve may result from infection as inflammatory cyst in correspondence with first and second mandibular premolars, while in the mandibular molars, the distance between the root apex and inferior alveolar canal should be in consideration. In the study by **Tilotta-Yasukawa et al 2006**, the distance of root apex of first mandibular molars from the inferior alveolar nerve varies from 1 and 4 mm and it is less than 1 mm with the second and third mandibular molars. For this reason, the spread of infectious cases to the inferior alveolar nerve that originates from apices of first or second mandibular molar may be quickly involved the nerve even if the periapical lesion size is small(**Rachele et al 2016**).

In infectious cases, the paresthesia can be the result of a combination of the following mechanisms.(1) *Mechanical Pressure*: In particular, the expanding infectious process can cause pressure on the nerve fibers. The pressure induces the paresthesia. (2) *Microbial Products*: in which the products of certain microbes (gram

negative bacteria) can puncture the perineurium with resultant nerve bundle impairment and soiled the conduction.

In view of these potential complications, several studies were conducted to assess the distances between inferior alveolar canal and the root apices of mandibular premolars and molars. However, most studies included only a limited number of specimens (**Kim et al 2010**) or were based on orthogonal and eccentric periapical radiographs or on panoramic radiographs. The value of such analyses is limited because of superimpositions of surrounding structures or distortions (**Bürklein et al 2015**). Although there is too many studies correlate the relation of third molars to inferior alveolar canal ,and also too many studies correlate the relation of molars to the buccal-lingual cortical bone. There is no relation of root apices of the mandibular premolars and molars to the inferior alveolar nerve in a sample of Egyptian population.

Cone-beam computed tomographic (CBCT) imaging provides 3-dimensional (3D) images with a moderate radiation dose (**Patel et al 2014**), and numerous studies have reported its value in diagnosing spatial relationships between anatomic structures (**Temple et al 2016; Tahmasbi et al 2017**). So spatial proximity of vital structures such as the inferior alveolar nerve, the incisive canal, and the mental foramen can be accurately assessed and measured (**Benavides et al 2012**). CBCT can overcome the limitations of radiographs by providing an accurate and 3D image of teeth and surrounding structures. CBCT scans were found to have an error less than that 0.6 % when measuring mandibular anatomy(**Ludlow et al 2007**). The advantages of CBCT are the weaknesses of 2D intraoral periapical and panoramic radiographic representations. The ability to visualize the area of interest and avoid superimposition permits accurate radiographic interpretation. So it is useful to assess the position of root apex of first and second premolar and mandibular molars to IAN. In other conventional radiographic techniques, there

are distortion and magnification of the anatomic structures ranging from 3.4% for periapical radiographs to more than 14% for panoramic radiographs (**Lazzerini et al 1996**).

Aim of the Study

The aim of the study is to assess the linear position between the roots of mandibular premolars and molars and the superior border of inferior alveolar canal.

Population: Adults, male and female from Egyptian population

Outcome Variable: Linear measurement of the distance between root apices of mandibular premolars and molars to the superior border of IAN.

	Outcome Measured	Measuring Device	Measuring Unit
Primary Outcome	Distance between root apices of mandibular premolars and molars to inferior alveolar canal	CBCT software Romexis®	Millimeters

Research question:

Among the mandibular premolars and molars, which roots are the closest to the inferior alveolar canal, in sample of Egyptian Population?

Materials and Methods

Study Design: Cross-sectional Study

Setting and Location:

- 1- The data collection will be obtained from the data base available at Oral & Maxillofacial Radiology department at faculty of Dentistry, Cairo University.
- 2- CBCT images will be obtained from Egyptian patients who had CBCT examination as part of their dental examination, diagnosis or treatment planning during the years 2018.

Participants:

A total of 162 CBCT scans of mandibular permanent premolars and molars belonging to Egyptian individuals are selected according to the following:

Inclusion criteria:

- First and second mandibular permanent premolars and molars of Egyptian patients starting from 18 years, males or females.
- Intact roots without fractures or cracks.
- Posterior teeth are present and their adjacent and opposing teeth.
- Absence of radiological evidence of dental malocclusion that could have altered the position of premolars or molars.
- CBCT scans of mandibular first and second premolars and molars using 20 x 10 cm FOV, 0.4mm voxel resolution.

Exclusion criteria:

- Evidence of apicectomy or periapical surgery.
- Odontogenic or non-odontogenic pathology.
- Congenital deformity of the mandible.
- External Root resorption.
- Previous history of fracture of the mandible.
- Tomographic images of poor quality or artifacts interfering with the detection of mandibular canal and apical morphology of the teeth.

Variables:

1. The crowding and overlapping of the mandibular posterior teeth .
2. Extraction of the adjacent or the opposing tooth may cause tilting of the tooth or over eruption of the opposing tooth.
3. Attrition of the teeth may cause over eruption of the teeth.
4. The presence of dental anomalies may influence the position of the tooth to the inferior alveolar canal.

Data Sources / Measurements:

Retrospective Data Analysis will be performed after the CBCT images are pooled from the computer database by convenient sampling technique.

CBCT images will be obtained from patients who required CBCT examination as part of their dental examination, diagnosis or treatment planning without exposing them to unnecessary radiation dose for the research purpose.

All the CBCT examinations are scanned by Planmeca Promax 3D®, 20 x 10 cm FOV, 0.4 mm voxel resolution, 90 kVp, 8 mA and 13.5 seconds exposure time.

To assess the shortest distance from the root apices to the border of the inferior alveolar canal, the multiplanar reconstruction view of the manufacturer's software viewer (Planmeca Romexis) with its axial, sagittal and coronal plane will be used, and the cross-sectional images through the mandible will be also used.

Cross sectional images will be oriented parallel to the long axis of the tooth, then the shortest distance from the deepest point of root apices and superior border of the inferior alveolar canal will be obtained to be examined (**Umut et al 2017**).

CBCT images will be interpreted by two oral radiologists independently; blinded from demographic data of the patients and from the results of each other.

All measurements will be assessed, once by the first investigator and then another time two weeks later for intra-observer reliability. The second investigator will assess the measurements once for inter-observer reliability.

Then inter-observational and intra-observational variability between the observers will be evaluated.

Bias:

No source of bias.

Study Size:

The aim of the study is to assess the relationship between the roots of mandibular premolars and molars and the superior border of inferior alveolar canal in Egyptian population. Based on the previous paper by **San Chong,et al,2017**,the prevalence of alveolar nerve 78%.Using a precision of 5, a design effect set at 1 with 95%CI(confidence interval), a total sample size of 162 will be sufficient. The sample size was calculated by Epi info.

Sampling Strategy: The sample will be collected by convenient sampling technique.

Statistical Methods:

Data will be analyzed using IBM SPSS advanced statistics (Statistical Package for Social Sciences), version 24 (SPSS Inc., Chicago, IL). Numerical data will be described as mean and standard deviation or median and range. Categorical data will be described as numbers and percentages. Comparisons between males and females for normally distributed numeric variables will be done using Student's t-test while for non-normally distributed numeric variables will be done by Mann-Whitney test. Comparisons between categorical variables will be performed using the chi square test. A p-value less than or equal to 0.05 will be considered statistically significant. All tests will be tailed.

References

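### The Bias section denies any source of bias, yet the 162 scans are a convenience sample with no rule for which eligible scans enter

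*Protocol*

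**What the plan says.** The Bias section consists of one statement: "No source of bias". Shortly after it, Sampling Strategy says: "The sample will be collected by convenient sampling technique". Data Sources / Measurements says the same of the database search: "Retrospective Data Analysis will be performed after the CBCT images are pooled from the computer database by convenient sampling technique".

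Setting and Location names the source. The scans come from a single department ("The data collection will be obtained from the data base available at Oral & Maxillofacial Radiology department") and from "Egyptian patients who had CBCT examination as part of their dental examination, diagnosis or treatment planning during the years 2018".

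Participants fixes the number and points to the eligibility criteria: "A total of 162 CBCT scans of mandibular permanent premolars and molars belonging to Egyptian individuals are selected according to the following". Those criteria include "Posterior teeth are present and their adjacent and opposing teeth" and "Absence of radiological evidence of dental malocclusion that could have altered the position of premolars or molars". Pathology, root resorption, previous mandibular fracture and poor-quality images are excluded. All scans use one machine and one setting. Two radiologists read independently and blinded, and one of them repeats the readings after two weeks.

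**The concern.** Convenience sampling from a clinical database can introduce selection bias, so a protocol that names this method cannot also say that no source of bias exists. If more than 162 scans from 2018 are eligible, somebody has to choose among them. The protocol does not say how.

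The primary outcome is a distance in millimetres, summarised as mean and SD or median and range, and the rationale section hopes the results will help reduce nerve injury. If the chosen scans differ systematically from those left out, the difference goes straight into the reported distances. Adding more scans chosen in the same way would not by itself remove it. A reader who relies on the Bias section is told there is no such limit.

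**Working it through.** **Step 1: what each safeguard controls.**

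| Provision in the protocol | Controls eligibility | Controls measurement | Decides which eligible scans enter |
|---|---|---|---|
| Inclusion and exclusion criteria | yes | in part (image quality) | no |
| One department, year 2018 | yes (source) | no | no |
| One scanner, one setting | yes | yes | no |
| Two blinded readers, repeat reading | no | yes | no |
| Convenience sampling | no | no | left open |

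No section gives a consecutive, date-ordered or random rule, and none says that all eligible scans are taken.

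**Step 2: can eligible scans still differ in ways that matter?** By the protocol's own account, yes. The Variables list names attrition and dental anomalies as features that may change tooth position, and neither is named in the eligibility criteria. The protocol gives no size for such an effect.

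**Step 3: how a selection difference enters the mean.** The protocol gives no figure for bias, so there is none to reproduce. Let N be the number of eligible 2018 scans, f = 162/N, m_in the mean distance in scans entered and m_out the mean in scans left out.

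- Mean of all eligible scans = f × m_in + (1 − f) × m_out
- Shift = m_in − mean of all eligible scans = (1 − f) × (m_in − m_out)

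Only the 162 comes from the protocol (Participants; Study Size). N and the difference m_in − m_out are not given, so the values below are **assumptions, not predictions**.

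| Assumed N | 1 − 162/N | Shift if difference is 0 mm | 0.2 mm | 0.5 mm |
|---|---|---|---|---|
| 162 or fewer | 0 (all taken) | 0 | 0 | 0 |
| 200 | 1 − 0.810 = 0.190 | 0 | 0.038 mm | 0.095 mm |
| 500 | 1 − 0.324 = 0.676 | 0 | 0.135 mm | 0.338 mm |
| 1,000 | 1 − 0.162 = 0.838 | 0 | 0.168 mm | 0.419 mm |

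The first factor keeps rising towards 1 as N grows, so with a large database almost the whole difference passes into the reported mean.

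**Step 4: scale.** The literature review cites apex-to-canal distances below 1 mm for second and third molars. The voxel size is 0.4 mm.

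**Step 5: what the calculation leaves out.** The formula compares the 162 with all eligible scans in the same department. It says nothing about how that department's patients differ from Egyptian adults in general. A shift common to all roots would leave their ranking unchanged. An effect on the ranking or on the comparison of males and females cannot be derived from the protocol.

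**The case against.** The strongest reply is that little of consequence is shown. The research question asks which roots lie closest to the canal, and a shift common to all roots does not alter that answer. The protocol openly states its convenience sampling, single centre, clinical indication and dentition criteria, and its Variables list names features that may move teeth. On this view the defect is one wrong sentence, and correcting it removes the contradiction. Every driver of the millimetre figures is assumed, the range includes zero, and five of the six non-zero shifts are below one voxel.

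Much of this is fair. The figures are illustrations, and no effect on the root ranking is claimed. Voxel size, however, does not bound the bias in a mean over many scans. Stating the sampling method elsewhere does not make the Bias section true. The distances themselves are the primary outcome, so the ranking is not all that matters.

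Two smaller points also stand:

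- **Scope wording.** The research question refers to a sample of the Egyptian population, while the Population line and the Study Size aim name that population without the limit. This is minor, and the conclusion does not depend on it.
- **The figure of 162.** A selection rule leaves this target in place, although the stated inputs give 1.96² × 0.78 × 0.22 / 0.05² ≈ 263.7, so 264. That is a separate issue; the rule works for whatever number is finally justified.

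**Conclusion.** The concern holds. The Bias section contradicts the sampling method fixed elsewhere in the protocol, and nothing says which eligible scans become the 162. Confidence in those two points is high, because both rest on the text alone. This is not detail left to an analysis plan: the protocol itself makes the incorrect statement and chooses the weaker method.

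The consequence is a possible shift in the reported distances, of unknown size and sign. It runs from zero to about 0.42 mm over the assumed range (N up to 1,000, difference up to 0.5 mm), and larger inputs would give more. The point should be corrected, but it does not by itself invalidate the study.

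**What to change.** 1. Replace convenience sampling with a stated rule: take eligible 2018 scans consecutively by date, or by simple random selection, until the target is reached. If fewer qualify, take them all.
2. Apply the eligibility criteria before any distance is measured, and log each exclusion with its reason.
3. Replace the Bias statement with the limits that remain: a single centre, patients with a clinical indication for CBCT, and the requirement that posterior, adjacent and opposing teeth be present.
4. Restrict the conclusion to that population, and use the same scope wording in the Population line, the research question and the Study Size aim.

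The cost is some extra screening time, which cannot be quantified because the number of 2018 scans is not given, and a narrower conclusion. No new scans or radiation exposure are needed. Date order may cover only part of 2018, and random selection first needs a list of eligible scans. Neither removes the single-centre and clinical-indication limits or the judgement involved in applying the criteria, so these must be disclosed.

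### The stated sample-size inputs give 264 scans, not 162; with 162 scans the 95% interval is about ±6.4 points, not ±5

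*Protocol*

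**What the plan says.** The calculation is in the protocol under Materials and Methods, Study Size. It takes its expected proportion from a previous publication, worded as "the prevalence of alveolar nerve 78" per cent, and continues: "Using a precision of 5, a design effect set at 1 with 95%CI(confidence interval), a total sample size of 162 will be sufficient". It names Epi Info as the software.

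The Participants section fixes the same number and shows that the unit is the scan: "A total of 162 CBCT scans of mandibular permanent premolars and molars belonging to Egyptian individuals".

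The protocol gives no unit for the precision. It gives no source population size, no finite population correction and no second set of inputs.

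**The concern.** A prevalence, a precision, a design effect and a confidence level are all that a precision-based sample size for one proportion needs, so the result can be checked directly. The printed result is far below what the printed inputs give.

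At stake is the credibility of the only argument for the study size. The paragraph says that 162 scans are enough for a precision of 5 at 95% confidence. If the inputs are right, that overstates the precision. If 162 came from other inputs, the paragraph misreports or omits one of them. In either case the calculation cannot be reproduced from the text.

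**Working it through.** **Inputs, all from Study Size**

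- Expected proportion p = 0.78.
- Precision d = 0.05. The text gives 5 without a unit; ±5 percentage points is the usual meaning in a prevalence calculation, and other readings are tested below.
- Design effect DEFF = 1.
- Confidence 95%, two-sided, z = 1.96.
- Stated result: 162.

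**Attempt to reproduce 162**

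n = DEFF × z² × p(1 − p) / d²

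n = 1 × 1.96² × 0.78 × 0.22 / 0.05² = 3.8416 × 0.1716 / 0.0025 = 263.7, rounded up to 264.

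The stated figure is not reproduced: 162 / 264 = 0.61, a shortfall of 102 scans.

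**Other readings of the stated inputs (n rounded up)**

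| Reading | n |
|---|---|
| 80% confidence | 113 |
| 85% confidence | 143 |
| 90% two-sided, or 95% one-sided | 186 |
| 97% confidence | 324 |
| 99% confidence | 456 |
| z rounded to 2 | 275 |
| Wilson interval, 95% | 262 |
| Continuity correction, 95% | about 284 |
| 5 as relative precision (d = 0.05 × 0.78 = 0.039) | 434 |
| 5 as total interval width (d = 0.025) | 1,055 |

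None gives 162. The alternative readings of the precision need more scans, so the missing unit does not explain the gap.

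**What does give 162**

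- *A different prevalence.* With p = 0.88 (or 0.12) and d = 0.05: 3.8416 × 0.88 × 0.12 / 0.0025 = 162.3.
- *A wider precision.* With p = 0.78 and d = 0.064, n is 160.9; the exact match is at d = 0.0638.
- *A finite population.* The finite-population form is n = DEFF × N × p(1 − p) / [(d²/z²)(N − 1) + p(1 − p)]. It gives 161.9 at N = 418 and 162.2 at N = 420, so N is about 419. With N = 999,999 it gives 263.6, which again rounds up to 264.

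The protocol states none of these.

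**What 162 scans deliver at p = 0.78**

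- Standard error: √(0.78 × 0.22 / 162) = 0.03255.
- 95% half-width: 1.96 × 0.03255 = 0.0638, or 6.4 points. The Wilson half-width is 6.3 points.
- Ratio to the claim: 6.38 / 5 = 1.28.
- Confidence of a ±5-point interval: z = 0.05 / 0.03255 = 1.536, which corresponds to about 87.6%.
- For comparison, the half-width at n = 264 is 0.04997, or 5.0 points.

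**The case against.** The strongest objection is the finite population. The scans come from one department's database for one year and then pass restrictive eligibility criteria, so a few hundred eligible scans is conceivable. If about 419 was entered as the population size, 162 follows with every printed figure unchanged, and the fault is an unreported input rather than a wrong one. That much stands: it cannot be said that one of the printed figures must be wrong. It does not rescue the paragraph, because no population size is given. The correction would also fit the text poorly. Study Size states its aim for the Egyptian population, not for one archive, and the correction assumes random sampling, whereas Sampling Strategy specifies convenience sampling.

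A second objection is that the 6.4 points describe a proportion that is not a named outcome. The primary outcome is a distance in millimetres, and Statistical Methods describes means or medians and comparisons by sex. This is fair: the shortfall does not show that the distance results are less precise, and 264 scans would not by itself justify the size for that outcome. That is a separate weakness of the calculation and does not correct its arithmetic.

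Third, the 88% is back-fitted. Nothing in the protocol supports it, and it serves only as a value to check against the Epi Info entry.

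**Conclusion.** The point holds. The stated inputs give 264 scans. The planned 162 is 61% of that and gives a 95% half-width of about 6.4 points in place of 5. Reaching 162 requires a changed prevalence, a wider precision or an unstated finite population of about 419.

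The conclusion assumes that the precision of 5 means ±5 percentage points and that no finite population correction applies. The first assumption is not critical, since the other readings tested need 434 or 1,055 scans. The second follows from the absence of any population size in the protocol. Because this paragraph is the only justification of the study size, it should be corrected.

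**What to change.** Check the values entered in Epi Info and change one sentence in Study Size accordingly.

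- **If the 78% is right and no finite population was used:** keep 162 and restate the precision, for example: with 162 scans and an expected proportion of 78%, the half-width of the 95% confidence interval is about 6.4 percentage points.
- **If another prevalence was entered** (88% would reproduce 162): correct the 78% and give its source.
- **If a finite population was entered** (about 419 would reproduce 162): state its size, and say that the precision then refers to that set of scans.

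In every case, give the unit of the precision. Only if ±5 points at 78% is a firm requirement does the number have to rise to 264, in both Study Size and Participants.

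The first three options cost one sentence and no extra scans; in the first, the stated precision becomes somewhat less favourable.

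### The research question asks which roots lie closest to the canal, but the only tests named for the distance compare males with females; no between-root contrast, interval or test is planned

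*Protocol*

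**What the plan says.** - **Aim of the Study:** "The aim of the study is to assess the linear position between the roots of mandibular premolars and molars" relative to the upper border of the canal.
- **Research question:** "Among the mandibular premolars and molars, which roots are the closest to the inferior alveolar canal, in sample of Egyptian Population". It is the only question posed.
- **Primary outcome (Aim of the Study table):** "Distance between root apices of mandibular premolars and molars to inferior alveolar canal", in millimetres.
- **Inclusion criteria:** scans cover first and second premolars and molars, with the condition "Posterior teeth are present and their adjacent and opposing teeth". One patient therefore contributes several roots.
- **Statistical Methods, description:** "Numerical data will be described as mean and standard deviation or median and range". The section does not say that the summaries are by root, and it gives no interval.
- **Statistical Methods, numeric tests:** "Comparisons between males and females for normally distributed numeric variables will be done using" Student's t-test; the same sentence gives Mann-Whitney for non-normal data.
- **Statistical Methods, categorical tests:** "Comparisons between categorical variables will be performed using the chi square test".

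The only 95% confidence interval in the protocol belongs to the sample-size calculation, for a proportion of 78%. The inter- and intra-observer evaluation compares readings, not roots.

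**The concern.** The question is about differences between roots, but the inference is aimed at differences between sexes. Sex appears in the population description and not in the aim, research question or outcome. Followed as written, the plan gives p-values for a contrast nobody asked about and answers its own question, at best, by ordering means or medians.

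That ordering would carry no statement of how sure it is, and the planned tables do not allow one to be worked out properly. The precision of a difference between two roots of one patient depends on the correlation between them, and means and SDs do not show it. Two roots a few tenths of a millimetre apart could then be reported as first and second closest when the data do not separate them. The two numeric tests named are also independent-samples tests, so reusing them between roots would ignore the pairing.

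**Working it through.** **1. Each planned analysis against the research question**

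| Planned analysis | Contrast | Answers the question? |
|---|---|---|
| Mean and SD, or median and range | none | ranking only, if tabulated by root |
| Student's t-test | males vs females | no |
| Mann-Whitney | males vs females | no |
| Chi-square | categorical variables, unnamed | no; the outcome is in mm |
| Observer variability | readings | no |

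The plan has no between-root figure of its own to reproduce.

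**2. Inputs for the size of the gap**

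- n = 162 scans (Participants; Study Size), taken as 162 patients each contributing both roots compared.
- The protocol gives no SD and no correlation. Both are assumed: SD 1.5 to 2.5 mm for single roots, SD 2 mm for differences, correlation ρ from 0 to 0.9.
- t(0.975; 161 df) = 1.975; √162 = 12.73.

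**3. One root.** Half-width of the 95% CI = 1.975 × SD / 12.73.

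- SD 1.5: 0.23 mm
- SD 2: 0.31 mm
- SD 2.5: 0.39 mm

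**4. Difference between two roots of the same patient, equal SDs.** SE = SD × √(2(1 − ρ)/162); half-width = 1.975 × SE. With SD = 2 mm:

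| ρ | SE (mm) | Half-width (mm) |
|---|---|---|
| 0 | 0.222 | 0.44 |
| 0.3 | 0.186 | 0.37 |
| 0.5 | 0.157 | 0.31 |
| 0.7 | 0.122 | 0.24 |
| 0.9 | 0.070 | 0.14 |

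Two data sets with identical means and SDs and a 0.3 mm gap would lead to opposite conclusions at ρ = 0.3 (0.37 > 0.3) and ρ = 0.7 (0.24 < 0.3).

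**5. Chance that two roots are ranked the wrong way round.** P = Φ(−d/SE), where d is the true difference. With SD = 2 mm:

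| d (mm) | ρ = 0.7 | ρ = 0.3 |
|---|---|---|
| 0.1 | Φ(−0.82) = 21% | Φ(−0.54) = 30% |
| 0.2 | Φ(−1.64) = 5% | Φ(−1.08) = 14% |
| 0.4 | Φ(−3.29) = 0.1% | Φ(−2.15) = 1.6% |

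**6. Which contrasts to adjust for.** The closest root is picked from the data, so adjusting only over contrasts with that root is not enough. In a simulation of six roots with equal means (10,000 runs, n = 162, paired t-tests), Holm over the 5 contrasts with the observed closest root gave at least one false claim in 10.4% of runs with all correlations 0.5. The figure was 9.2% with correlation 0.8 within a molar and 0.4 otherwise. Holm over all 15 pairs gave 3.8% and 3.7%.

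**The case against.** The best defence is that the study is descriptive. It is cross-sectional, sampled by convenience and sized for precision, and it states no between-root hypothesis. A per-root table does say which roots are closest in this sample. Covariance structure, multiplicity and handling of side are usually left to a statistical analysis plan, which may exist but is not at hand. Nothing calls the sex comparison primary or excludes other analyses, and the retrospective measurements allow a paired analysis later.

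Much of that is fair, and it is why the data are not at risk. It does not remove the mismatch. The protocol has its own Statistical Methods section, plans testing at p ≤ 0.05, and attaches both numeric tests to a contrast outside the research question. That is an analysis fixed on the wrong target, not a detail deferred.

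The size can also be challenged. The only distances in the protocol (Review of literature, one cited anatomical study) are 1 to 4 mm for first molars and under 1 mm for second and third molars. Read as ranges of individual values, they cap the SD at (4 − 1)/2 = 1.5 mm and 1/2 = 0.5 mm. With SD 1 mm, every SE in step 4 halves, and a true 0.2 mm difference is reversed in only 0.05% (ρ = 0.7) to 1.6% (ρ = 0.3) of samples. The doubtful gaps of 0.1 to 0.3 mm are also below the 0.4 mm voxel, although means can resolve less than one voxel. So the problem is confined to closely placed roots, such as perhaps two roots of one molar, for which the protocol gives no figure.

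Finally, SDs alone give a conservative bound (0.44 mm at SD 2) if correlations are not negative. That bound needs an assumption and does not replace a paired contrast.

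**Conclusion.** The concern holds and should be fixed. The mismatch rests on the text alone: the question is between roots, the named numeric tests are between sexes, and no between-root difference, interval or test appears anywhere in the protocol.

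The millimetre figures are illustrative. They rest on an assumed SD and correlation and on complete pairs from 162 patients, and they shrink in proportion if the true SD is smaller. Large differences between roots would be ranked correctly under the present plan; close ones could be reported as findings without support.

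**What to change.** Rewrite the analysis paragraph in Statistical Methods as follows.

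- **Primary analysis:** a within-patient comparison of distance (mm) across roots. One option is a linear mixed model with root as a within-patient factor, patient as the clustering unit, and a covariance structure that allows unequal correlations between roots (for example unstructured). Repeated-measures ANOVA is an alternative, or Friedman with paired follow-up tests if the distribution requires it.
- **Reporting:** the estimate and 95% CI for each root, using the same summary statistic for every root. Give pairwise differences with multiplicity adjustment over all root pairs, not only those involving the observed closest root.
- **Sex comparison:** label it secondary.
- **For the sponsor to confirm:** the list of roots (six roots give 6 × 5/2 = 15 pairs; four teeth give 4 × 3/2 = 6), and how side is handled (averaged, or a second within-patient factor).

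The cost is one paragraph and slightly more analysis work in SPSS 24, on measurements already planned. Adjusted intervals are wider: with Bonferroni over 15 pairs, SD 2 mm and ρ = 0.5, the critical value rises from 1.975 to 2.980 and the half-width from 0.31 to 2.980 × 0.157 = 0.47 mm.
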